## 6.5 Study Completion

Participants will be considered to have completed the study if they have completed all study measures for the final visit. The target window for the final visit is 24 months ± 6 weeks post-randomization. Further treatment of each study participant, including lifestyle and pitavastatin, will be directed by the participant's responsible physicians.

### 7. SAFETY ASSESSMENTS AND MONITORING

### 7.1 Specification of Safety Parameters

Given the study population and the potential for the presence of obesity-related co-morbidities which share similarities with adverse events (AE's) associated with statins, safety has been included as a secondary study aim, and is a prime consideration in this trial. The number and percentage of participants experiencing Adverse Events (AEs) and Serious Adverse Events (SAEs) will be summarized by system/organ class and by treatment group.

## 7.2 Recording and Reporting Adverse Events

A major component of safety monitoring is ascertainment and reporting of adverse events, including adverse drug reactions. The approach to these activities for this study is summarized in the sections that follow.

**7.2.1** Definitions of Adverse Event, Suspected Adverse Reaction, Adverse Reaction and Unanticipated Problems The FDA Final Rule on IND Safety Reporting Requirements [http://edocket.access.gpo.gov/2010/pdf/2010-24296.pdf] provides the following definitions:

- Adverse event: any untoward (e.g. unfavorable, negative, or harmful) medical
  occurrence associated with the use of a drug in humans, whether or not the event is
  considered drug related. An event can be any unfavorable and unintended sign,
  symptom, or disease temporally associated with the use of the product.
- Suspected Adverse Reaction: any AE for which there is a reasonable possibility that the drug caused the event, meaning the event is possibly, probably, or definitely related to the study drug.
- Adverse Reaction: an AE for which there is a greater degree of certainty regarding causality; meaning the event is probably or definitely related to the study drug. Adverse reactions are a subset of Suspected Adverse Reactions.
- Unanticipated Problem (UP): An UP is any incident, experience, or outcome involving risk to participants that meets all of the following criteria:
  - Unexpected in nature, severity, or frequency (i.e. not described in study-related documents such as the IRB-approved protocol or consent formetc.)
  - Related or possibly related to participation in the research (i.e. possibly related means there is a reasonable possibility that the incident experience, or outcome may have been caused by the procedures involved in the research)
  - Suggests that the research places participants or others at greater risk of harm (including physical, psychological, economic, or social harm).

#### 7.2.2 Classification of Adverse Events

Monitoring AEs requires that they be classified as to seriousness, expectedness, and potential relationship to the study drugs, all of which drive the reporting process.

#### a. Seriousness

Serious Adverse Event (SAE) is one that:

- Results in death,
- Is life-threatening (the participant was, in the view of the Principal Investigator, in immediate danger of death from the event as it occurred),
- · Requires inpatient hospitalization or prolongation of existing hospitalization,
- Results in persistent or significant incapacity or substantial disruption of the ability to conduct normal life functions,
- Is a congenital anomaly/birth defect in the offspring of a participant, or
- Is an Important Medical Event that may jeopardize the participant or may require medical/surgical intervention to prevent one of the serious adverse event outcomes.

The Common Terminology Criteria for Adverse Events (CTCAE) Version 4.0 MedDRA 12.1 (http://ctep.cancer.gov) provides a grading system that is used to categorize the severity of adverse events, as follows:

Grade 1 Mild transient, requires no special treatment or intervention,

does not interfere with daily activities

Grade 2 Moderate alleviated with simple treatments, may limit daily

activities

Grade 3 Severe requires therapeutic intervention and interrupts daily

activities

Grade 4 Life-threatening

Or disabling

Grade 5 Death

A SAE, as defined above, encompasses CTCAE grades 4 and 5, and any Grade 3 event that

requires or prolongs hospitalization, or that substantially disrupts the ability of the participant to conduct normal life functions.

## b. Expectedness

The purpose of reporting is to provide new, important information on serious reactions or events previously unobserved or undocumented. Therefore, all AEs will be evaluated as to whether their occurrence was unexpected, using the following definitions:

- Unexpected: An unexpected AE or adverse reaction is one for which the nature or severity is not consistent with information in the protocol, consent form, or product brochure. An AE or adverse reaction also may be categorized as unexpected if the event has not previously been observed at the same specificity and/or severity.
- Expected: An event is considered expected if it is known to be associated with the study drug(s) and/or the disease state. For this protocol, expected events reported since market introduction regardless of evidence of causality and included in the product brochure are:
  - o Myalgia, muscle spasms, pain in extremity, back pain, arthralgia, rhabdomyolysis
  - Asthenia, hypoesthesia, fatigue, malaise, dizziness, insomnia, depression, headache, weakness
  - o Diarrhea, constipation, dyspepsia, nausea, abdominal pain
  - Hepatitis, jaundice, fatal and non-fatal liver failure
  - Diabetes
  - o Pruritis, rash, urticaria
  - Interstitial lung disease
  - Erectile dysfunction
  - Rare post-marketing reports of cognitive impairment

## c. Causality

Causality assessment is required to determine which events require expedited reporting. The following criteria will be used to determine causality:

- Not Related: The event is clearly related to other factors, such as the participant's clinical state, or non-study drugs or interventions.
- Possibly Related: The event follows a compatible temporal sequence from the time of administration of the study drug, but could have been produced by other factors such as the participant's clinical state or non-study drugs or interventions.
- Probably Related: The event follows a reasonable temporal sequence from the time of drug administration, and cannot be reasonably explained by other factors such as the participant's clinical state, or non-study drugs or interventions.

### 7.2.3 Identification of and Data Collection Procedures for Adverse Events

AEs that are not considered adverse reactions or suspected adverse reactions will be identified when they are reported to the clinical center or during scheduled study visits by study coordinators and investigators. AEs will be assessed using self-report, physical examination data, and medical record review.

### 7.2.4 Reporting Procedures (Table 2)

Fatal or life-threatening AEs are to be reported to the DCC within 24-hours of first knowledge of the event. Those that are unexpected and considered possibly, probably, or definitely related to the study drug will be reported by the DCC to the FDA, the DSMB Chair, the MM, the NHLBI, and all study Investigators as soon as possible, but no later than 7 calendar days after first knowledge of the event, followed by a complete report within 15 calendar days. All other fatal or

life threatening events that are unrelated to study drug will be reported semiannually to the DSMB and the NHLBI, and annually to the FDA.

All other *SAEs* (*i.e.*, *non-fatal* or *not life-threatening*) that are unexpected and considered possibly, probably, or definitely related to the study drug will be reported to the DCC within 24-hours of learning of the event. The DCC will report the event to the FDA, NHLBI, DSMB and all study Investigators within 15 calendar days after first knowledge of the event.

All other *AEs* not meeting the criteria for expedited reporting will be reported to the DCC within 7 calendar days of first knowledge of the event. The DCC will report these AEs quarterly to NHLBI and annually to the FDA.

**Table 2. Reporting of Adverse Events** 

Seriousness	Reporting Timeframe
Fatal or life threatening	Within 24-hours of learning of the event
Serious, but not fatal or life threatening, and pregnancy	Within 24-hours of learning of the event
All other	Within 7 calendar days of learning of the event

## 7.2.5 Reporting Adverse Events to Institutional Review Boards for NIH-Supported Multi-Center Clinical Trials

The site investigator or designee is responsible for reporting all serious adverse events to the local IRB in accordance with local policies and procedures.

### 7.2.6 Follow-up of Participants after Adverse Events

For AEs with a causal relationship to the study drug, follow-up by the Investigator is required until the event or its sequelae resolve or stabilize at a level acceptable to the Investigator.

### 7.3 Safety Monitoring

The Data and Safety Monitoring Plan for this trial will follow standard PHN monitoring principles. Oversight of data and safety is provided by the PHN Data and Safety Monitoring Board (DSMB), appointed by NHLBI. The DSMB meets at least twice a year to review data on AEs, adverse reactions, suspected adverse reactions, patient-reported outcomes, data quality, and study recruitment at regular intervals, and makes recommendations about study conduct to the NHLBI.

A DSMB Summary Report, summarizing the DSMB's findings, will be prepared within 30 days of each meeting and distributed to each Principal Investigator and Study Coordinator to be forwarded to the local IRB.

The DSMB and NHLBI are assisted by an independent Medical Monitor in reviewing serious adverse events in PHN studies. The PHN MM is the NHLBI's designee for determining causality and expectedness of all SAEs.

### 8. STATISTICS

## 8.1 Statistical Analysis Plan

The primary analytic approach for all trial outcomes will be intention-to-treat (ITT). Several secondary analytic approaches will also be examined as outlined below and discussed in detail in a separate Statistical Analysis Plan (SAP).

- Non-intention-to-treat (NITT): Participants will be classified according to treatment
  actually received. NITT analyses, while potentially more powerful due to less dilution of
  treatment effect compared to an ITT analysis, are subject to bias because the inherent
  balance and lack of bias provided by randomization in measured and unmeasured
  patient characteristics of the two treatment groups is not preserved.
- Non-intention-to-treat by duration of pitavastatin use: If a substantial fraction of
  participants either cross-over from placebo to pitavastatin or are prescribed open-label
  pitavastatin or other statin therapy by their treating physicians, analysis will be
  conducted with 'time-under-statin' as a continuous or stratifying (categorical) predictor of
  change in the outcomes.
- Exclusion of ineligible participants: Secondary analyses will be conducted after exclusion of participants who were later found to have been ineligible at the time of randomization.
- Covariate-adjusted analysis: adjustment for baseline (pre-randomization) factors known to be associated with a particular outcome can increase the efficiency of the treatment effect comparison. Such factors will be identified from the literature and used as covariates in the trial outcome analyses.

Descriptive statistics will be used to determine the distribution of values for all variables, and variables requiring transformation to meet analytic assumptions will be appropriately transformed. Data analysis plans will be keyed to the specific aims as follows, and incorporate appropriate methodology as described below.

## 8.1.1 Analysis of the Primary Outcome

The analytic approach for the Primary Outcome is summarized here. The detailed plan for all planned outcomes is provided in the Statistical Analysis Plan (SAP).

Primary Aim: To compare the effect of pitavastatin versus placebo on vascular measures in at least 354 adolescents with excess adiposity (body mass index [BMI] ≥85th percentile) and CDO (defined as high non-HDL-C + high TG/HDL-C ratio).

**Primary Hypothesis:** Over 2 years of observation, participants in the pitavastatin group will have a significantly different change over time (slope) in pulse wave velocity (PWV) than participants in the placebo group.

**Study Measures:** Pulse wave velocity (PWV); secondary measures include carotid intima media thickness (CIMT) and carotid artery stiffness.

**Primary Analysis:** Change in each of the vascular variables will be compared between groups across all study time points using SAS for Windows® (SAS Institute, Cary, NC).

## 8.1.2 Pre-Specified Sub-Group Analyses

It is of interest to determine whether the effect of statin therapy vs. placebo differs across subgroups. The pre-specified subgroups for analysis of all primary and secondary outcomes are:

- Age at baseline (stratified by deciles)
- Gender
- Race
- Baseline insulin resistance (HOMA-IR) (stratified by deciles)
- Baseline BMI percentile (stratified by deciles)
- Family history of premature CVD

Subgroup by treatment group by time interaction tests will be performed to test whether the treatment effect is homogenous across subgroups. Statistical testing within subgroup will not be conducted unless the interaction test p-value is  $\leq 0.05$ .

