## 8.2 Number of Participants to be Enrolled

The sample size for the study will be at least 177 participants randomized per group (at least 354 total randomized). The hypothesis is that vascular status as assessed by PWV will be improved by statin therapy. Specifically, there will be a significant group (drug vs. placebo) by time interaction effect on mean PWV in a repeated measures analysis appropriately controlled for participant and clinical site specific random effects.

Although reports of longitudinal measures or clinical trials using PWV in youth are nonexistent, our investigators reported data from lean and obese youth age 10-24 years who were age, race, and sex matched using the same SphygmoCor device proposed for this study. In 241 lean participants (BMI <85th%ile), carotid-femoral PWV was 5.4 (0.7) compared with 6.3(1.1) in 234 non-diabetic obese participants (BMI ≥95th%ile). Obese youth had PWV 14% greater than lean youth. Two statin trials used PWV measured by the same SphygmoCor system to provide baseline and end of study vascular data for adults (average age 50s). In 20 adults with rheumatoid arthritis treated with simvastatin for 6 weeks, PWV dropped from 9.6 (2.3) at baseline to 8.9 (2.1), a 7.4% decrease from baseline. In 35 hypercholesterolemic adults treated with rosuvastatin plus low-fat diet for 4 weeks, PWV dropped from 9.5 (1.9) to 7.8 (1.5), a decrease of 18% from baseline.

Sample size was computed under several scenarios based on different values for the group by time interaction effect size in the 2 treatment groups (statin and placebo/no drug) assuming baseline PWV 6.3±1.1 m/sec and, based on unpublished data from [name] et al. collected 5-years apart on 268 obese youth, a correlation within participants for repeated measures over time of 0.5 [observed value from [name] et al. was 0.68]; alpha 2-sided = 0.05, power (1-beta) = 0.85, equal n for each group, equal assignment to treatment group at each clinical center and no stratification factors beyond treatment group, as follows:

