### **Assumptions:**

- 1. Baseline pulse wave velocity (PWV) is normally distributed with a mean of 6.3 m/sec and a standard deviation of 1.1 m/sec.
- 2. In addition to the baseline PWV measurement, PWV will be measured at after six months, 12 months, and 24 months.
- 3. Any change in PWV over the two-year duration of the study is conservatively assumed to be linear in time (i.e., 25% of the change will be observed at the six month visit, 50% of the change will be observed at the 12 month visit, and 100% of the change will be observed at the 24 month visit).
- 4. The following 3 hypotheses (scenarios) are considered:
  - a. In Scenario 1, the PWV will remain unchanged in the control group over the twoyear duration of the study and will decrease 8% in the statin group over the same 2-year period.
  - b. In Scenario 2, the PWV will decrease 5% in the control group over the two-year duration of the study and will decrease 11% in the statin group over the same 2-year period.

- c. In Scenario 3, the PWV will remain unchanged in the control group over the twoyear duration of the study and will decrease 5% in the statin group over the same 2-year period.
- 5. The within-participant correlation between any pair of PWV measurements is assumed to be 0.5.
- 6. The sample size is adjusted by 20% to account for participant dropout.
- 7. The effect of crossover has not been incorporated into these sample size calculations.

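### Cutting age, HOMA-IR and BMI percentile into deciles leaves about 14 completers per arm per cell; continuous modifier terms would answer the subgroup question more efficiently

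*Protocol*

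**What the plan says.** Protocol Section 8.1.2 names six subgroup variables. Three are continuous and are to be cut into ten groups: "Age at baseline (stratified by deciles"), HOMA-IR in the same way, and "Baseline BMI percentile (stratified by deciles"). The scope is broad: "The pre-specified subgroups for analysis of all primary and secondary outcomes are" these six. Homogeneity of the treatment effect is tested by a subgroup-by-treatment-by-time interaction, and tests within a subgroup are allowed only when the interaction p-value is 0.05 or less. The section gives no reason for ten groups and mentions no trend or continuous version.

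Section 8.2 sizes the trial for the main group-by-time effect on PWV: "The sample size for the study will be at least 177 participants randomized per group (at least 354 total randomized"), with "alpha 2-sided = 0.05, power (1-beta) = 0.85, equal n for each group" and an allowance of 20% for dropout. It contains no power statement for interactions.

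**The concern.** Section 8.1.2 asks whether the statin effect differs across patient types. For age, insulin resistance and adiposity, the natural form of that question is a gradient, such as more effect with higher HOMA-IR. A test that treats ten ordered groups as unordered spreads one gradient over nine contrasts and so uses the data inefficiently. The individual cells are also small. If an interaction test reaches 0.05, the protocol permits tests in cells too small to say much about the size of the effect in any one of them. What is at stake is how informative the pre-specified subgroup analyses can be, not the primary result.

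**Working it through.** **Inputs (protocol Section 8.2).** 177 randomized per arm; 20% dropout; "Baseline pulse wave velocity (PWV) is normally distributed with a mean of 6.3 m/sec and a standard deviation of 1.1 m/sec"; "The within-participant correlation between any pair of PWV measurements is assumed to be 0.5"; baseline plus follow-up visits ("PWV will be measured at after six months, 12 months, and 24 months"), coded t = 0, 0.25, 0.5, 1 in two-year units; Scenario 2 effect of 6% of 6.3 = 0.378 m/s over two years.

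**Reproducing the plan's figure.** The mean of t is 0.4375 and SS_t = 0.1914 + 0.0352 + 0.0039 + 0.3164 = 0.5469. Slope variance = 1.1² × (1 − 0.5) / 0.5469 = 1.106, so slope SD = 1.052, as printed. A two-sample t-test with difference 0.378, SD 1.052, two-sided alpha 0.05 and 85% power needs 141 completers per arm. 141 / 0.8 = 176.25, which rounds up to the stated 177.

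**Cell size.**
- Completers: 177 × 0.8 / 10 = 14.2 per arm per decile.
- If every randomized participant contributed fully: 177 / 10 = 17.7.

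**Precision within a decile**, half-width = 1.96 × √(2 × 1.106 / n):
- n = 14.16: ±0.77 m/s, or 2.05 times the planned 0.378.
- n = 17.7: ±0.69 m/s, or 1.83 times.
- Whole trial, n = 141.6: ±0.25 m/s.

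Power to detect 0.378 m/s inside one decile is about 16% with 14.16 per arm and about 19% with 17.7.

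**Interaction power.** Section 8.1.2 does not state degrees of freedom. Ten unordered levels with linear time give (10 − 1) × 1 = 9. Assume the treatment effect changes linearly with the modifier.
- The variance of the 1-df interaction slope per SD of modifier is 4 × 1.106 / 283 = 0.01564. Power of 80% needs a noncentrality of 7.85, which is a slope of 2.80 × √0.01564 = 0.35 m/s per SD.
- Decile grouping keeps 96% (normal modifier) to 99% (uniform modifier) of a linear signal, so the noncentrality becomes 7.53 to 7.77. On 9 df this gives power of 43% to 44%. A simulation of 4,000 trials with 282 completers gave 80.0% for the continuous term and 40.6% for the deciles.
- For 80% power the 9-df test needs a noncentrality of 15.65. 15.65 / 7.85 = 2.0 times the sample.

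**How the ratio moves.** With F tests and a normal modifier, 9-df power divided by 1-df power is 0.41 when 1-df power is 50%, 0.52 at 80%, 0.62 at 90% and 0.70 at 95%.

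**A more modest modifier.** At 0.189 m/s per SD (half the planned effect), the 1-df test has about 33% power and the 9-df test about 13%.

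**The case against.** Several points on the other side are sound.

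- **The 9 df is an inference.** Section 8.1.2 gives no coding. Scoring the deciles 1 to 10 and testing a trend would be a 1-df test with 78% to 80% power where the continuous term has 80%, so almost nothing would be lost. An unordered test is the natural reading of a homogeneity test across subgroups, but it is not stated, and the SAP, which was not available here, may add detail. Visits entered as categories would instead give 27 df.
- **The power comparison is conditional.** It rests on roughly linear modification. For a U-shaped pattern, a linear term alone could do worse than deciles.
- **The benchmark is large.** 0.35 m/s per SD means an effect of about 0.03 m/s at one SD below the mean and 0.73 at one SD above. For smaller gradients, the trial is weak with any method.
- **Fourteen per arm is a completer count.** A repeated-measures analysis uses partial data, hence the range up to 17.7. With the observed correlation of 0.68 that Section 8.2 also cites, the half-widths fall to 0.55-0.62 m/s. That is still well above 0.378.

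A reader might infer that BMI percentile makes poor deciles because values crowd towards 100. The documents do not support this. Deciles depend only on rank, and a z-score from the same age- and sex-specific reference ranks participants as the percentile does. The protocol also gives no BMI distribution beyond the entry threshold. The ceiling matters only once percentile is used as a continuous term.

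A reader might also infer that the trial will present ten noisy estimates as subgroup findings. The protocol does not say so. It gates within-subgroup tests, calls no interaction test confirmatory, and in Section 8.3 undertakes to report the number of comparisons and the possibility of chance significance.

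**Conclusion.** The point stands as an inexpensive improvement to the subgroup analyses. The decile cut is fixed in the protocol, and the small cells follow from its own figures whatever test is used: about 14 completers per arm per decile, at most about 18, with a half-width roughly twice the planned effect. The power loss, 43-44% against 80%, holds if the deciles are unordered, time is linear and modification is roughly linear.

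It would go too far to say that the deciles always halve the power, or that they alone would make the trial miss real effect modification. The ratio depends on the true effect, and a trial sized for its main effect has low power for modest interactions under either method.

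**What to change.** Amend Section 8.1.2 so that age, HOMA-IR and BMI are each tested as a continuous baseline variable with a 1-df treatment-by-time-by-modifier term. Transform HOMA-IR if it is skewed. Put BMI on an uncapped scale such as the z-score, because percentile is bounded at 100 once used continuously. Add a low-df spline for each modifier as a check for non-monotone modification, and use a few broad groups such as tertiles for display only.

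The cost is a wording change in the protocol, with matching SAP text; no new data, visits or participants are needed. The downside is that a non-monotone pattern is less visible without the spline.
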